## 5.2 Study Population

### 5.2.1 Treatment Group Patient Selection

Adult male and female patients will be consecutively screened for the study. Eligible patients must meet all of the inclusion criteria and none of the exclusion criteria.

The Treatment Group includes 60 study patients.

### **5.3 Withdrawal and Lost-to-Follow-Up**

Patients may be withdrawn from the study for any of the following reasons:

- Lost-to-follow up despite exhaustive attempts to contact. A minimum of three (3) attempts to contact such patients must be made. One such attempt must include a registered return receipt requested letter. All attempts to contact the patients must be documented.
- Patients may voluntarily decide to withdraw from the study. All reasonable attempts should be made to ascertain the reason for voluntary withdrawal.
- It is in the best interest of the subject to be withdrawn from the study

All patient withdrawals must be documented on the **Study Completion/Exit Case Report Form (CRF)**.

### **5.4 Duration of Study**

Approximately 2-3 patients are seen per month at the University of Washington who may be eligible for B-TEVAR. It is possible that this number will increase in time if the protocol proves safe and effective. It will likely take 18-24 months to recruit 60 patients. Treatment Group patient follow-up visits will occur at 30 days, 6 and 12 months post-implant, and then annually through five years. Subjects who undergo only the TEVAR procedure will be followed at 30 days, 12 months and annually thereafter through 5 years. Therefore, study duration is estimated to run approximately 6-7 years.

## **6.0 STUDY PROCEDURES**

The study will be monitored in accordance with written standard operating procedures consistent with 21CFR812. Treatment of patients enrolled in this study will include tests and procedures listed in **Appendix IV: Schedule of Activities**.

### **6.1 Patient screening**

Prospective candidates are evaluated in a consecutive manner for eligibility for the study at the time they are considered to be candidates for TAAA repair. Initial screening may include diagnostic testing (e.g., imaging, angiogram, laboratory testing, and a physical examination) performed as part of routine medical care.

The following steps outline the process to determine patient eligibility for enrollment. There will be no need for shipment of ANY devices as these devices are currently available off the shelf and are modified according to the procedure described herein for the physician modified graft. The commercially manufactured grafts will be shipped from the Cook center in Australia where they are manufactured

1. Ensure that patient has signed an IRB approved **INFORMED CONSENT FORM**
2. Complete the **INCLUSION/EXCLUSION WORKSHEET**
3. Complete the **DEVICE PLANNING AND SIZING WORKSHEET**

As patients will be enrolled via two pathways, single or two-stage, the following flow diagram will show the breakdown:

#### Step 1: Principle Investigator Evaluation

The PI will perform a history and physical examination and review any pertinent pre-operative studies, including the CT angiogram. Based on this review, the PI will make a determination as to whether or not the patient meets the inclusion/criteria, whether they are “high risk” for open repair, whether the aneurysm anatomy is amenable to repair with B-TEVAR, and whether a single or two-staged procedure is appropriate.

The decision about single vs. staged procedure will be individualized to each subject. The determination will depend on length of aortic coverage, size of the aneurysm, and access anatomy. A single staged procedure is preferable in cases with short aortic coverage (lower risk of spinal cord injury and coagulation abnormalities), large aneurysms (at increased risk of interval rupture), and subjects with difficult access (as re-operation may be complicated by re-operative / difficult access). In each case, the PI will attempt to balance these issues to optimize patient safety and minimize risk. There are insufficient data at this time to prescribe absolute parameters to this decision process, and the decision must be based on best physician judgment.

As discussed in section 4.0.3, device selection will be made based on a balance of the urgency of treatment as well as the specific patient anatomy. For patients requiring urgent treatment, (i.e. those with very large aneurysms or those presenting with symptoms concerning for impending rupture) or patients who must travel long distances and cannot make multiple trips, the physician modified device or the pre-manufactured t-Branch device would be used. The physician modified device is customizable and can be used in small aortic flow channels and can be deployed from femoral access only. The t-Branch device, on the other hand, has downward oriented cuffs which may facilitate implantation in a large aneurysm sac, but it requires brachial artery access. For patients who are deemed to be able to wait the 6-8 weeks for graft manufacture and can make the requisite multiple trips to the University of Washington, they will be treated with the commercially manufactured custom device. It is expected that a majority of subjects will be treated with the commercially manufactured custom device.

#### Step 2: Cardiac Intensivist Evaluation

In order to obtain a second opinion about the safety and effectiveness of the B-TEVAR procedure, all patients who the PI believes would be eligible will be reviewed by a second attending physician experienced in the care of patients with aneurysmal disease. The physicians

who will serve in this role are the attending physicians who staff the cardiothoracic intensive care unit. These physicians are experts in the peri-operative and post-operative care of patients undergoing complex cardio-thoracic and vascular operative procedures. They have extensive experience in the assessment of such patients.

Patients, who the PI believes are appropriate B-TEVAR candidates, will be seen then by the Cardiothoracic Intensive Care Unit (CT ICU) physician. The CT ICU physician will have an opportunity to review the patient's studies, interview and examine the patient. Based on this evaluation, the CT ICU physician will determine 3 things:

- a) Whether or not the patient has a reasonable expectation of surviving the B-TEVAR procedure
- b) Whether or not the patient has a reasonable expectation of survival beyond 1 year with successful repair
- c) Whether or not the patient is high risk for open repair as defined in the Inclusion criteria Section 5.1.1

If the CT ICU physician concurs with the PI that the patient meets all 3 of the above criteria, then the patient will move forward to Step 3.

The CT ICU physician will not determine technical aspects of the B-TEVAR procedure, as they are not experts in the planning or conduct of the procedure itself. Their role is to provide an unbiased, experienced, assessment of the patient's physiologic reserve and life expectancy. As there are no validated tools for estimating patient survival, the study will rely on agreement between two experienced physicians, the PI and the CT ICU physician. These two attending physicians must agree that all 3 of the above criteria have been met by the subject in order to proceed with enrollment. If the PI and CT ICU physician are not in agreement that all 3 criteria are met by the subject, that subject will not be enrolled.

### Step 3: Study Enrollment

Subjects who meet all 3 criteria listed in Step 2, as determined by both the PI and the CT ICU physician, will be provided the opportunity to participate in the study. Signed written consent will be obtained and subject will enroll in the study.

### Step 4: Procedure

The patient will then proceed to have their procedure. The process will differ for single vs. two-staged procedures.

- A) For single staged patients, this first operation will be the B-TEVAR procedure. Their post-operative follow up will follow the protocol as described below, with clinic visits, labs and imaging done at 1, 6, 12 months and annually to 5 years. The B- TEVAR Follow up CRF will be used.

B) For two-staged patients, this first operation will be the TEVAR procedure. Their post-operative follow up will utilize the TEVAR Follow Up CRFs. They will be seen with imaging studies at 1 and 12 months and annually until 5 years or until they proceed with the B-TEVAR second stage. After the patient undergoes the B-TEVAR procedure, they will continue with the routine study follow up at 1, 6, 12 months and annually to 5 years after the B-TEVAR procedure using the B-TEVAR Follow Up CRFs.

The decision to proceed with the second stage will be at the discretion of the PI. That determination will be based on when the patient has returned to their pre-operative level of functional status, their laboratory values have stabilized/recovered, they remain free from major organ system dysfunction as a consequence of the first stage, and the patient agrees to undergo a second operation. If the patient's recovery is complicated by a permanent decline in functional status, or permanent organ system dysfunction (e.g. long term nursing facility residency, permanent spinal cord injury, end-stage renal failure on dialysis), then the PI will determine that the second stage should not proceed. These patients will then continue follow up using the TEVAR CRF until their condition improves and they can undergo the B-TEVAR procedure or they complete 5 years of follow up. As described below in the Risk Analysis, section 10.0, such patients who do not complete the second stage will be left with an incompletely treated aneurysm and will remain at risk of rupture and death. This will be explained in detail to the subjects prior to enrollment.

Step 1

PI Evaluation:

- a) Meet all Inclusion and no Exclusion Criteria
- b) High risk for open repair
- c) Anatomically eligible for B-TEVAR
- d) Single vs. multiple staged repair

Step 2

2nd Attending Physician Evaluation:

- a) Patient has a reasonable expectation of survival after operation
- b) Patient has a reasonable expectation of survival to 1 year with successful repair
- c) Patient high risk for open repair

Step 3

Informed Consent Obtained  
Subject Enrolled in B-TEVAR Study

Step 4

Single Stage Repair:

- a) B-TEVAR procedure done
- b) Follow up using B-TEVAR Follow up CRF at 1, 6, 12 months and annually to 5 years

Planned 2-Stage Repair – 1st stage:

- a) First stage TEVAR procedure done
- b) Follow up with TEVAR follow-up CRF at 1, 12 months and annually to 5 years or until undergo 2nd stage
- c) Determination to proceed to 2nd stage per PI based on clinical evaluation as

2-Stage Repair – Complete 2nd stage:

- a) B-TEVAR procedure done
- b) Follow up as described for single stage repair in protocol: B-TEVAR Follow up CRF at 1, 6, 12 months and annually to 5 years

2-Stage Repair – Incomplete:

- a) Follow up using TEVAR CRF at 1, 12 months and annually to 5 years

## 6.2 Pre-procedure evaluation

The following assessments will be performed no more than three months prior to the B-TEVAR implant/surgical procedure unless otherwise noted:

- Patient demographics
- Past Medical History/Past Surgical History
- Physical exam
- Concomitant medications (anticoagulants, antiplatelets, antibiotics, statins, Beta blockers and ACE inhibitors only)
- Laboratory testing, which includes renal and coagulation assessments, hematocrit as well as serum pregnancy for female patients of childbearing potential (with the exception of the serum pregnancy test which will be performed within one week of the procedure)
- Contrast enhanced CT scan for aneurysm measurement and device planning. CT scan must be performed within 4 months of the implant date.

If the patient is eligible to be enrolled into the study, the results of these screening assessments are recorded on the **Baseline CRF** and the **Device Sizing and Planning Worksheet**. If a patient does not qualify for enrollment into the study, the baseline screening worksheets will be retained, together with the patient's signed/dated consent(s). The subject will be considered a Screen Failure.

## 6.3 Treatment period (surgical procedure)

The following assessments and data collection will be performed at the time of the implant/surgical procedure:

- Investigational device accountability- documentation of product information (e.g., lot number, serial number)
- Exact measurements of position and configuration of custom made fenestrations
- Type of anesthesia
- Anticoagulation
- Description of delivery system access on both ipsilateral and contralateral sides (e.g. femoral cut down, percutaneous access, closure device)
- Volume of contrast used
- Total fluoroscopy time during procedure
- Estimated blood loss and replacement requirements
- Size of stents in visceral vessels
- Adjunctive procedures (e.g. stent placement)
- Investigator assessment of TAAA device performance as it relates to:
  - Access success/failure, delivery/deployment success, evidence of endoleak, device integrity issues
- Adverse events

The above events will be recorded on the **Procedure – System Evaluation CRF (either TEVAR alone or B TEVAR CRF)**

#### 6.4 Pre-Discharge

The following assessments and testing will be performed post-procedure, prior to discharge:

- Physical exam
- Laboratory testing, which includes renal function and optional complete blood cell counts and coagulation studies
- Length of ICU and hospital stay
- Concomitant medications (anticoagulants, anti-platelets, antibiotics, statins, Beta blockers and ACE inhibitors/ARBs only)
- Adverse events
- Other relevant data as indicated on the CRF, including optional wound assessment.

The above assessments are recorded in the **Hospital Discharge CRF**. In some instances, patients may experience a prolonged hospitalization post procedure. In those cases, the above assessments should be performed no more than two (2) weeks post procedure.

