## 9.2 Secondary Endpoints

### 9.2.1 Safety

The following secondary safety endpoints will be evaluated at 30 days, 12 months and annually to 5 years:

- All-cause mortality
- TAAA Related Mortality
- Freedom from permanent spinal cord injury
- Major Adverse Events (MAE)
- TAAA rupture
- Surgical conversion

The CEC will meet annually to review all MAE. All deaths that occur in the study will be adjudicated by the CEC. TAAA related death is any death determined by the CEC to occur as a result of the initial procedure (first 30 days or prior to hospital discharge), TAAA rupture, conversion to open surgical repair, or due to secondary intervention after B-TEVAR.

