### **9.3 Clinical Utility Measurements**

The following Clinical Utility measurements associated with both the B-TEVAR and the TEVAR alone will also be assessed:

- Conduit use
- Amount of blood loss
- Days spent in ICU
- Days spent in hospital
- Type of Anesthesia
- Placement of lumbar drain
- Rationale for planned staged approach and for any patient who is unable to undergo a second stage
- Discharge status to home, nursing facility, and assessment of functional status

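### Section 6.4 times the discharge assessments, including length of stay, at two weeks for prolonged admissions and names no later step to complete ICU days, hospital days or discharge status

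*Protocol*

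**What the plan says.** Protocol section 6.4 (Pre-Discharge) opens with the normal timing: "The following assessments and testing will be performed post-procedure, prior to discharge". Six items follow: physical examination, laboratory tests, "Length of ICU and hospital stay", concomitant medications, adverse events, and a general line for other data on the form. The form is then named: "The above assessments are recorded in the" Hospital Discharge CRF.

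The section goes on to the exceptional case: "In some instances, patients may experience a prolonged hospitalization post procedure". The rule for it is: "In those cases, the above assessments should be performed no more than two (2) weeks post procedure".

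Section 9.3 (Clinical Utility Measurements) lists "Days spent in ICU" and "Days spent in hospital", with no time limit on either, as well as discharge status (home or nursing facility) and functional status. The Protocol Summary also lists ICU stay and length of hospital stay without a limit.

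**The concern.** A total stay cannot be known while the subject is still admitted. The two-week rule covers every item on the list, and length of stay is one of them. Applied as written, it asks for that item while the admission is still open. What goes on the form is then days so far, which is a right-censored value. It looks the same as a completed stay unless someone marks it or updates it later.

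The rule applies only to prolonged admissions, so any error falls on the long stays and always in the same direction, towards a shorter recorded stay. Section 10.0 names reduced hospitalization as a potential benefit of endovascular repair, so the error would run in favour of that claim. Discharge status in section 9.3 has the same difficulty, because it does not exist until the subject leaves.

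**Working it through.** The protocol states no figure for length of stay, so there is nothing to reproduce. The check has two parts: whether another place in the protocol repairs the gap, and how large the effect could be.

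**1. Is there a later step that completes the stay?**

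- Section 6.5 (follow-up at 1, 6 and 12 months and annually) lists examination, laboratory tests, CT, imaging assessment, medications and adverse events, plus a general line for other data on the CRF. It does not name length of stay or discharge date.
- Appendix IV (Schedule of Activities) has no row for length of stay or discharge date at any visit.
- Section 9.3 names the measures but not when they are recorded.

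The only openings are the general lines for other CRF data in 6.4 and 6.5. The CRF is not shown.

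**2. What value results?**

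Let L be the number of days from procedure to discharge. If the form is completed at day 14 and not updated, the recorded value is min(L, 14). An earlier assessment would give a smaller value. ICU days are affected only for subjects who are still in the ICU at the assessment or return to it afterwards. The figures below are for hospital days.

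**3. Size without a distributional assumption**

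Inputs: N = 60 (section 5.0), one admission counted per subject, and k subjects who each stay d days beyond day 14 (assumed).

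Understatement of the mean = k × d / N

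- k = 6, total stay 30 days (d = 16): 6 × 16 / 60 = 1.6 days
- k = 12, total stay 30 days (d = 16): 12 × 16 / 60 = 3.2 days
- k = 3, total stay 24 days (d = 10): 3 × 10 / 60 = 0.5 days
- k = 15, total stay 44 days (d = 30): 15 × 30 / 60 = 7.5 days

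**4. Size under an assumed lognormal stay**

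With median m and log-standard deviation s, and Φ the standard normal distribution function:

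- share beyond day 14 = 1 − Φ((ln 14 − ln m) / s)
- true mean = m × exp(s² / 2)
- capped mean = true mean × Φ((ln 14 − ln m − s²) / s) + 14 × share

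| m (days) | s | Share > 14 days | Subjects of 60 | True mean | Capped mean | Bias |
|---|---|---|---|---|---|---|
| 6 | 0.6 | 0.079 | 4.7 | 7.2 | 6.8 | −5% |
| 6 | 1.0 | 0.198 | 11.9 | 9.9 | 7.1 | −28% |
| 8 | 0.8 | 0.242 | 14.5 | 11.0 | 8.5 | −23% |
| 10 | 0.6 | 0.287 | 17.2 | 12.0 | 9.8 | −18% |
| 10 | 1.0 | 0.368 | 22.1 | 16.5 | 9.3 | −43% |

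In every row the share beyond day 14 is below one half, so the median does not move. The mean does, as do the maximum and any percentile that lies beyond day 14. If stay is completed at actual discharge, all of these biases are zero.

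**The case against.** The best reply is that the cap is inferred. The text says the assessments should be done within two weeks. It does not say that stay is recorded as 14 days, frozen, or barred from update. Strict literalism also proves too much: the whole list is to be done before discharge, so even an ordinary subject's final stay would strictly be unknown when recorded. The natural reading is that the limit times the bedside items, while a duration is completed on a form named for discharge. Section 9.3 asks for discharge status, which already presupposes data taken at discharge.

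Part of this stands. The protocol does not mandate truncation, and the unseen CRF may allow later completion. But in an ordinary admission the assessment falls close to discharge and little is lost. In a prolonged one, weeks may remain, and this is the case for which the text fixes an earlier time without exempting length of stay. That section 9.3 needs discharge data shows that 6.4 does not fit it; it does not supply the missing step.

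A reader might infer three stronger things that the documents do not support:

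- **That no recorded stay can exceed 14 days.** The limit runs from the procedure. The protocol does not say which day starts the count of hospital days, so pre-procedure days may be added, and the form may be updated.
- **That adverse events after day 14 are lost.** Sections 8.9 and 8.10 record them on a separate Adverse Event CRF, and section 6.5 and Appendix IV collect them again at 1 month and at later visits. The 30-day major adverse event endpoint does not depend on the discharge form.
- **That in-hospital deaths after day 30 would be misclassified.** Section 9.2.1 does use "first 30 days or prior to hospital discharge" in defining aneurysm-related death. But the Clinical Events Committee adjudicates every death, and nothing ties its decision to the length-of-stay field. Section 11.7 makes admission and discharge summaries available for monitoring.

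**Conclusion.** The point holds as a minor one. Section 6.4 fixes a time for recording length of stay that, followed literally, gives an incomplete value for the longest admissions, and no listed later step completes it. The measures affected are hospital days, ICU days for subjects still in or returning to the ICU, and discharge status.

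The size cannot be derived from the protocol. Under the lognormal assumptions (median 6 to 10 days, log-standard deviation 0.6 to 1.0), about 5 to 22 of 60 subjects would still be in hospital after day 14, and mean hospital stay would be understated by about 5% to 43%. These figures assume that the form is completed at day 14 and never updated. If sites already complete it at discharge, the effect is nil and only the wording is at fault.

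The measures are neither primary nor secondary endpoints, the study has no comparator arm, and no stated decision rule uses them. That keeps the point minor.

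**What to change.** Revise the last sentence of section 6.4 so that the two-week timing in prolonged hospitalizations applies only to the physical examination, laboratory tests, concomitant medications and the adverse-event check. Add that ICU days, hospital days and discharge status are completed on the Hospital Discharge CRF at actual discharge or in-hospital death.

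The cost is a sentence or two of text. No visit, test or treatment decision changes, and the dates should already be in the hospital record. If the CRF already works this way, the edit only brings the protocol into line with it. For subjects already enrolled with a prolonged stay, the field can be checked against the discharge summary.

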#### 6.5 Post-Treatment follow-up period

The following assessments and tests will be performed at the following intervals:

Time period post-treatment	Acceptable visit timeframe allowance
1 Month (30 days)	± 14 days
6 Months (180 days)	± 30 days*
12 Months (365 days)	± 45 days
Annually from 2 to 5 years	± 60 days

\*This will not be done for those undergoing TEVAR only

- Physical exam
- Laboratory testing to assess renal function and, if needed, to measure CBC
- Contrast Enhanced Spiral CT of the Chest/Abdomen/Pelvis OR for patients unable to receive IV contrast, a non-contrast thin cut CT scan of the Chest/Abdomen/Pelvis will be performed as well as a duplex of the abdominal aorta to assess the branch patency, velocity and to look for the presence of endoleak and aneurysm sac size (\* for subjects undergoing the TEVAR first stage, no aortic duplex will be performed)
- Device/aneurysm assessment based on imaging (endoleak, migration, integrity, patency, TAAA dimensions)
- Concomitant medications - anticoagulants, anti-platelets, antibiotics, statins, Beta-blockers and ACE inhibitors/ARBs
- Adverse events
- Other relevant data as indicated on the CRF including optional wound assessment.

The above assessments are recorded in the appropriate **Follow-up CRF**.

All subjects who have undergone the B-TEVAR device implantation, whether in a single or multiple stage will be followed with the B-TEVAR Follow-up CRF and will be analyzed as a

single group as well as by subgroup of device type. The date of implantation of the modified device will serve as the start time for follow up. Subjects who do not undergo the second stage of a planned staged repair will be analyzed separately and evaluated for survival and cause of death. With the exception of data points specific to the branched graft (i.e. branch complications, migration, etc.) the same clinical data points will be recorded for patients who only undergo the first stage of a staged repair, including medical demographics, aneurysm size and extent, and major adverse events. Additional information for the TEVAR alone will include a rationale as to why the second stage was not completed. For the two staged approach, the time interval between Stage 1 and Stage 2 will be recorded. Complete data will be reported for each group. Outcomes based on subgroup analysis of those who had single repair, staged repair and those who only had the initial stage and did not complete the second stage will also be reported.

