### **2.1.1 Observation**

If an aortic aneurysm is small and not causing symptoms, the treating physician may perform an ultrasound, a CT or MRI scan every 6 to 12 months to assess changes in the size or shape of the aneurysm. Along with serial radiographic measurement, optimal medical therapy is instituted. This includes smoking cessation, blood pressure control, and administration of aspirin and a statin (cholesterol lowering medication that may slow the rate of aneurysm growth). Observation is usually used for aneurysms that are smaller than 5-6 cm in diameter, fusiform in shape, and those that are growing slowly,  $\leq 10\%$  per year. If the TAAA is large, irregular in shape, rapidly expanding, or is causing symptoms, it will require prompt treatment to prevent death due to rupture of the aneurysm.

Most patients with TAAA also have advanced medical co-morbid illnesses. In one large study, 40% of patients with TAAA referred to the major aortic center in Scotland were deemed unfit for open repair due to the severity of their medical illnesses. This number is likely an underestimate, as the most medically ill were not referred. Fifty-five percent of untreated patients had died by a median of 12 month follow up, half due to rupture.

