## APPENDIX IV: SCHEDULE OF ACTIVITIES

Procedure	Baseline	Treatment	Discharge	1 Month Follow-Up	6 Month Follow-Up 	12 Month Follow-Up	Annual Follow-Up
Medical/Surgical History	X 						
Physical Exam	X 		X	X	X	X	X
Spiral Contrast Enhanced CT	X 			X 	X 	X 	X 
Laboratory Assessment (creatinine, PT, PTT, INR, CBC)	X 		X 	X 	X 	X 	X 
Adverse Event Assessment		X	X	X	X	X	X
Concomitant Medication Assessment (anticoagulants, antiplatelets, antibiotics, ACE inhibitors, Beta blockers and statins only)	X		X	X	X	X	X
Device/aneurysm assessment based on imaging (endoleak, migration, integrity, patency)				X	X	X	X

 CBC, PT, PTT and INR are optional after Baseline.

 Baseline med/surgical history, physician exam performed no more than 3 months prior to the implant/surgical procedure.

 Laboratory assessments performed no more than 3 months prior to surgical/implant procedure

 Serum pregnancy HCG test for females of childbearing potential performed no more than one week prior to surgical/implant procedure

 Baseline contrast enhanced CT must be obtained within 4 months of anticipated treatment date.

 If subject not able to tolerate contrast enhanced CT, a non contrast CT and visceral branch duplex ultrasound can be performed

 Subjects who undergo TEVAR only will not have the 6 month visit

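### First-stage-only subjects have no scheduled adverse-event assessment between months 1 and 12, so some major adverse events may go unrecorded in those who die or are lost in that interval

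*Protocol*

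**What the plan says.** The reduced schedule is stated consistently in the body of the protocol. Section 5.4: "Subjects who undergo only the TEVAR procedure will be followed at 30 days, 12 months and annually thereafter through 5 years". The visit table in Section 6.5 marks the 6-month row: "This will not be done for those undergoing TEVAR only". Appendix IV repeats it in a footnote to the 6-month column: "Subjects who undergo TEVAR only will not have the 6 month visit". That column carries the adverse-event assessment as well as the imaging. For the branched repair, the flow diagram under Section 6.1 Step 4 reads: "Follow up using B-TEVAR Follow up CRF at 1, 6, 12 months and annually to 5 years".

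On data and reporting, Section 6.5 sets aside items specific to the branched graft. It then says "the same clinical data points will be recorded for patients who only undergo the first stage of a staged repair", and names major adverse events among those items. It adds: "Subjects who do not undergo the second stage of a planned staged repair will be analyzed separately and evaluated for survival and cause of death". Outcomes by pathway are also to be given, including "those who only had the initial stage and did not complete the second stage will also be reported".

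Two other places bear on this:
- Section 6.6 covers unscheduled visits for an issue associated with the device. It lists reasons related to the B-TEVAR procedure and records only data pertinent to the reason for the visit.
- Appendix IX (Data Safety Monitoring Plan), Section 1.3, cites follow-up at 30 days, 6 months and 12 months as a protection against risk. It makes no exception for TEVAR-only subjects.

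**The concern.** The protocol asks for the same MAE information in each pathway group but looks for it less often in one of them. The whole 6-month visit is dropped, not just the branch imaging that would be irrelevant without a branched graft. A first-stage-only subject who dies or is lost between the two visits has no scheduled assessment after month 1.

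The fallback in Section 6.6 does not clearly cover a stroke, myocardial infarction or renal failure treated elsewhere in someone who never had B-TEVAR. Care elsewhere is plausible, since Section 4.0 says that some patients travel very long distances.

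At stake is the descriptive reading of MAE components across single-stage, completed staged and first-stage-only repair. If non-fatal events are found less completely in the third group, its profile looks somewhat better than it was.

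**Working it through.** The protocol states no figure on this point, so there is none to reproduce. The check has three parts.

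**1. Gaps between scheduled adverse-event assessments.** Inputs are the Section 6.5 visit days and windows: day 30 ± 14, day 180 ± 30, day 365 ± 45.

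| Group and interval | Nominal (days) | Shortest | Longest |
|---|---|---|---|
| First-stage-only, month 1 to 12 | 365 − 30 = 335 | 320 − 44 = 276 | 410 − 16 = 394 |
| B-TEVAR, month 1 to 6 | 180 − 30 = 150 | 150 − 44 = 106 | 210 − 16 = 194 |
| B-TEVAR, month 6 to 12 | 365 − 180 = 185 | 320 − 210 = 110 | 410 − 150 = 260 |

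**2. Which MAE figures can be affected.**
- *Subjects who die before month 12.* Death is a listed MAE (Sections 8.11 and 9.1.1), so each already counts in the any-MAE proportion. Only a non-fatal component before death can be missed.
- *Survivors seen at month 12.* Intervening events can be recorded then.
- *Subjects lost before month 12.* Any MAE after the month-1 visit can be missed.
- *Endpoint times.* Section 9.2.1 reads MAE at 30 days, 12 months and annually, never at 6 months. Both groups have a visit at each of those times.
- *Primary endpoints.* Sections 9.1.1 and 9.1.2 count from the branched procedure, so first-stage-only subjects are outside both.

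**3. Illustrative size, deaths only.** The protocol gives no mortality for this group. As assumptions, take the 25% in Section 2.0 (one-year rupture deaths in patients unfit for surgery) and the figure in Section 2.1.1 ("Fifty-five percent of untreated patients had died by a median of 12 month follow up, half due to rupture") as 12-month mortality m. With a constant hazard h = −ln(1 − m)/365 and S(t) = exp(−ht), the share of all subjects dying between day 30 and day 365 is d = S(30) − S(365):
- m = 25%: d = 0.227
- m = 55%: d = 0.486

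Let q be the assumed chance of a non-fatal MAE before such a death. If nothing else captures it, the share of the group losing a non-fatal component is d × q:

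| m | q = 5% | q = 20% |
|---|---|---|
| 25% | 0.227 × 0.05 = 1.1% | 0.227 × 0.20 = 4.5% |
| 55% | 0.486 × 0.05 = 2.4% | 0.486 × 0.20 = 9.7% |

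The protocol gives no size for the group. If 5 to 15 of the 60 subjects were first-stage-only (an assumption), the loss is between 5 × 1.1% ≈ 0.1 and 15 × 9.7% ≈ 1.5 subjects.

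For the effect of a 6-month contact, use monthly time, h = −ln(1 − m)/12. Among those alive at month 1, the share with no later assessment is 1 − exp(−11h) = 23% to 52% now, and 1 − exp(−5h) = 11% to 28% with the contact. The longest nominal gap falls from 335 to 185 days.

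**The case against.** The strongest reply is that recording does not depend on visits. Section 8.9 defines adverse events without reference to visits. Stroke, infarction, paralysis and renal failure would ordinarily be serious under Section 8.10. Section 12.2 has the Clinical Events Committee adjudicate all serious events whatever their relation to the device, and Section 9.2.1 has it adjudicate all deaths. Section 5.3 requires at least three contact attempts before a subject is lost, and Section 6.7 asks for a final assessment at discontinuation. The reduced schedule is deliberate, and no between-group MAE test is described. The groups are also defined by what happened after treatment, and B-TEVAR follow-up starts at implantation of the branched device, so a 6-month call would not make them comparable.

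Most of this stands, and it keeps the point small. It does not show how the site would learn of a non-fatal event treated elsewhere. The committee can adjudicate only what has been reported, and Section 6.6 is too narrow to close that gap.

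Two stronger readings are tempting, and the documents support neither:
- *MAEs are under-counted in this group.* This does not follow, because deaths count as MAEs, survivors can report at month 12, and other routes of capture exist.
- *This is the group expected to die most often before month 12.* The protocol says only that subjects who do not complete the second stage remain at risk of rupture (Sections 6.1 Step 4 and 10.0), and it calls the risk between stages unknown. Section 2.1.4 describes a mixed group that includes subjects found able to tolerate open repair. The 25% and 55% come from unfit or untreated patients, not from patients who had a first-stage TEVAR.

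**Conclusion.** The asymmetry is real. For a nominal 335 days, first-stage-only subjects have no scheduled adverse-event assessment, although Section 6.5 requires the same MAE data and reports by pathway. The consequence is possible under-recording of non-fatal MAE components in those who die before month 12, and of any MAE in those lost before then. The any-MAE proportion among subjects who die, the survivors seen at month 12 and both primary endpoints are not affected.

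The size is small and bears only on description: about 1.1% to 9.7% of the group through deaths. That range rests on borrowed mortality, an assumed non-fatal risk of 5% to 20%, a constant hazard and no other capture. Losses to follow-up would add to it by an amount the documents do not allow one to estimate. Separately, Appendix IX Section 1.3 does not match the visit schedule for these subjects. The point is minor but cheap to improve.

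**What to change.** - In Sections 5.4, 6.1 Step 4 and 6.5 and in Appendix IV, waive only the 6-month clinic visit and imaging for subjects who at that time have had only the first stage. Keep a 6-month adverse-event and vital-status contact by telephone or record review.
- Extend Section 6.6 so that any interim adverse event in a TEVAR-only subject is recorded, whether or not it relates to the device or to B-TEVAR.
- Reconcile Appendix IX Section 1.3 with the visit schedule.

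The cost is a wording amendment and a little coordinator time for a subset of 60 subjects, with no added imaging. The MAE figure in this subgroup may become slightly less favourable. The contact evens out when events are looked for, but it does not make the pathway groups comparable in other respects.
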